7.1 Safety Reviews

A DMC review may consist of the evaluation of (1) all AEs, (2) ADEs relevant to potential subject safety issues, (3) case reviews of subjects with reported SAEs, and (4) summary tables of all safety endpoints (Section 4.4).

Following a meeting, the DMC will provide timely recommendations to the Windtree study team. Recommendations may consist of, but not be limited to the following:

- Continue the study as planned
- Suspend study enrollment, pending additional information
- Close study enrollment

An unmasked independent statistician, not a member of the committee, will be responsible for the statistical analysis of the data.

8 STUDY PROCEDURES AND GUIDELINES

A table of study procedures and activities is presented in Section [1.2](#).

Before conducting any study-related activities, a signed written ICF must be signed and dated by the subject's legally authorized representative (Section [12.2](#)).

8.1 Vital Signs and Gas Exchange Parameters

8.1.1 Vital Signs

Vital signs (body temperature, respiratory rate, and heart rate) will be documented at randomization (\pm 5 minutes) and every 30 (\pm 5) minutes until study treatment initiation (active or sham).

Vital signs will be recorded:

- Study Days 1-3: time 0 (T_0 ; study treatment initiation), 10, 20, 30, 40, 50, 60, 70, 80, 90, 100, 110, 120, 130, 140, 150 minutes (\pm 3 minutes) after initiation; 3 \pm 0.5, 6 \pm 1, 9 \pm 1, 12 \pm 1, 18 \pm 2, 24 \pm 2, 36 \pm 2, 48 \pm 2, 60 \pm 2 and 72 \pm 2 hours after initiation.
- Repeat study treatments: treatment initiation, 10, 20, 30, 40, 50, 60, 70 minutes (\pm 3 minutes) after initiation.
- Study Days 4-7: daily at 0800 and 2000 hours (\pm 2 hours)

During study treatment administration, except T_0 , temperatures will not be recorded. If timing for measurements overlap, only one measurement should be taken.

8.1.2 Gas Exchange Parameters

Oxygen (O_2) saturation for each subject will be monitored by pulse oximetry (SpO_2); PCO_2 will be assessed for each subject by a transcutaneous monitor (eg, SenTec). Values for gas exchange parameters (PCO_2 , FiO_2 , SpO_2) and PEEP will be documented at randomization (\pm 5 minutes) and every 30 minutes following randomization until study treatment initiation (active or sham). The transcutaneous monitor must be calibrated for accuracy against a blood gas value (arterial, capillary, or venous) at the time of initial set-up and recalibrated, as necessary, in accordance with local institutional practices to ensure accuracy of the monitor output.

Gas exchange parameters will be recorded:

- Study Days 1-3: time 0 (T_0 ; study treatment initiation), 10, 20, 30, 40, 50, 60, 70, 80, 90, 100, 110, 120, 130, 140, 150 minutes (± 3 minutes) after initiation; 3 ± 0.5 , 6 ± 1 , 9 ± 1 , 12 ± 1 , 18 ± 2 , 24 ± 2 , 36 ± 2 , 48 ± 2 , 60 ± 2 and 72 ± 2 hours after initiation.
- Repeat study treatments: treatment initiation, 10, 20, 30, 40, 50, 60, 70 minutes (± 3 minutes) after initiation.
- Study Days 4-7 for FiO_2 and SpO_2 : daily at 0800 and 2000 hours (± 2 hours).
- Final Visit: FiO_2

If timing for measurements overlap, only one measurement should be taken.

8.2 Physical Examination

A complete physical examination will be performed by the PI or designee. The designee must be a member of the site-based staff qualified to performed physical exams (such as a nurse practitioner or physician assistant); physical examinations performed at screening must be reviewed and approved by the PI. Any new, clinically significant abnormal physical examination findings at the final period must be documented as AEs in the eCRF.

At the one-year corrected age follow-up, an abbreviated physical exam should be performed and recorded in the eCRF.

8.3 Chest Radiograph

A chest radiograph for the diagnosis of RDS and exclusion of air leak may be performed to assist in the screening assessment but is not required. However, a chest radiograph is required prior to dosing to confirm the diagnosis of RDS and to rule out other conditions. A radiograph obtained in the course of clinical management may be used in lieu of obtaining samples specifically for this study. A blinded review of all radiographs may be performed by Windtree or designee.

A chest radiograph will be required for study subjects who are intubated for any indication during the first 7 study days, if the procedure does not delay or compromise the emergent care of the subject.

8.4 Demographics

Demographic information (gestational age, sex, race, ethnicity) will be recorded at screening.

8.5 Maternal, Birth, and Medical History

The subject's relevant medical information will be recorded at screening, including the following:

- Maternal history, including rupture of membranes (time relative to birth, type), presence of clinical chorioamnionitis, use of antenatal steroids (number of doses)
- Birth history, including date and time of birth, mode of delivery (vaginal, Caesarian section), single or multiple birth (number), Apgar score (assessed at 1 and 5 minutes of life), presence of congenital anomalies, birth weight in grams, use of sustained inflation resuscitation technique
- Medical history, from birth to randomization

8.6 Concomitant Medications

Concomitant medications and therapies required for the general care of the subject are permitted, except for investigational agents, investigational medical devices, or any SRT before randomization (see also Section 8.6.1).

All concomitant medication and concurrent therapies will be documented from birth until the time the subject completes the primary phase of the study (36 weeks PMA), is discharged from the hospital, dies, or is transferred to another hospital (Section 10.2). Dose, route, unit, frequency of administration, indication for administration, and dates of medication will be captured on the eCRF.

For the long-term follow-up period, information on bronchodilators, steroids, and palivizumab (Synagis®; MedImmune, LLC, Gaithersburg, MD, USA) will be collected.

8.6.1 Use of Additional Surfactant Replacement Therapies

Following randomization, commercially available SRT may be administered to subjects whose respiratory status has deteriorated such that conventional SRT is in the subject's best medical interest in the judgment of the investigator (ie, "rescue surfactant"). Because conventional SRT requires endotracheal intubation (even if a tube other than an endotracheal tube is used, such as a thin catheter), subjects receiving commercially available SRT will be considered intubated and to have respiratory failure due to RDS (see Section 4.3.1). Such subjects remain in the study and are followed until study completion but will not receive study treatment.

8.6.2 Use of Caffeine Citrate or Systemic Corticosteroids

Use of caffeine citrate or other methylxanthines is recommended and will be recorded as with any other concomitant medication.

Use of prenatal steroids is permitted. Postnatal steroids are not permitted unless a clear medical need is determined.

8.7 Respiratory Support and Oxygen Delivery

8.7.1 General Principles for Respiratory Support

For the purposes of this study, nCPAP refers to any device which maintains a constant airway pressure above ambient pressure and uses a patient interface on the subject's face (eg, nasal prongs, mask). Non-invasive ventilation (NIV) refers to any device which generates a constant or variable positive pressure and uses a patient interface on the subject's face (see also Section 8.7.4). Therefore, nCPAP is a form of NIV with a constant airway pressure, while SiPAP, non-invasive positive pressure ventilation (NIPPV) and IPPB would be examples of NIV with variable pressures. The study nCPAP device is the specific bubble nCPAP device and interface supplied by Windtree for use with the ADS.

MV refers to any device which generates a constant or variable positive pressure via an endotracheal tube or tracheostomy. For this study, MV using a non-invasive interface will be considered non-invasive ventilation. Oxygen-only support refers to delivery of oxygen without the generation of pressure above ambient pressure (eg, standard-flow nasal cannula).

Study subjects are to be maintained on study nCPAP from the time of randomization until at least 6 hours after they have completed delivery of either treatment as outlined in Section 8.7.3. The management of respiratory support (including nCPAP) and oxygen delivery is otherwise at the discretion of the study PI, keeping in mind that repeat treatments of lucinactant for inhalation can be delivered only on study bubble nCPAP.

The study definition of respiratory failure due to RDS (Section 4.3.1) is used for categorization and analysis purposes only; it is not intended to mandate or guide clinical decision making.

8.7.2 Emergent Respiratory Support

Emergent endotracheal intubation and MV, in accordance with local institutional guidance, must be initiated at any time if deemed necessary for subject safety. Masking may be broken, if necessary, for subject safety.

Any clinical event indicating a need for MV, additional ventilatory support, or increases in oxygen must be evaluated as a potential AE (Section 8). If it is determined that the event qualifies as an AE, it must be reported in the study eCRF as such.

8.7.3 Use of Nasal Continuous Positive Airway Pressure

Study treatment may be delivered only via the study interface and nCPAP device, known as “bubble nCPAP.” Subjects are to remain on study nCPAP for at least 6 hours following each study treatment; 24 hours is strongly recommended, and ideally the subject will remain on study nCPAP until 36 hours following randomization (when re-dosing is no longer permitted). If a subject is switched from study nCPAP to an alternate form of NIV within 6 hours of dosing, the reason will be documented in the eCRF.

Changing to an alternate form of nCPAP or other form of NIV in absence of escalating respiratory support requirements may on occasion be necessary but is discouraged for a number of reasons. First, there are currently no definitive data to support that any form of NIV produces superior outcomes to any other form when used as a primary support modality. Second, each change in modality results in transient removal of positive airway pressure from the subject, which may cause alveolar derecruitment and subsequent respiratory deterioration, thereby presenting a safety risk. Third, use of modalities other than study nCPAP may pose a disincentive to administer repeat treatments, since to do so would require changing back to study nCPAP, which carries the risk of derecruitment as described, as well as additional logistical burden.

The study nCPAP device and patient interface is commercially available and FDA-registered. On-site study and clinical staff will be trained by Windtree (or a qualified designee) on the use of the study nCPAP and interface. All local institutional policies and procedures relevant to the administration and safety surveillance of nCPAP must be followed in conjunction with study specified procedures and assessments and in accordance with good clinical practice and judgment. During the nCPAP delivery, subjects must be monitored for complications related to placement of the patient interface.

Procedures that may optimize nCPAP delivery include ensuring proper placement of the patient interface, inserting an oro- or nasogastric tube, maintaining the subject’s neck position in a mild extension that is comfortable for the subject, using pacifiers or chin strap, and suctioning the mouth and nose as needed.

Initial nCPAP settings will depend on the subject’s clinical condition. Should the subject require increased respiratory support, incremental increases in FiO₂ (to a maximum of 0.45) or nCPAP

should be made by 1 cm H₂O until a maximum nCPAP of 8 cm H₂O is achieved. If a sustained nCPAP of > 8 cm H₂O or FiO₂ ≥ 0.45 are necessary to maintain an SpO₂ of 90% to 95% or if PCO₂ > 50 mmHg, then other forms of respiratory support may be employed. If unsuccessful, the subject should be evaluated for clinical signs and symptoms consistent with respiratory failure due to RDS (Section 4.3.1) and treated accordingly.

8.7.4 Use of Non-Invasive Ventilation

In subjects eligible for this study, NIV must be implemented within 30 minutes of birth. In the delivery room, intermittent positive pressure breaths may be administered manually or mechanically through a non-invasive patient interface (eg, mask or nasal prongs) for no longer than 10 minutes. Following delivery, any mode of NIV or non-invasive oxygen support may be used to support respirations as clinically indicated. However, if part of the unit's standard of care, it is strongly recommended that potential subjects are initiated with bubble nCPAP to minimize the number of changes and time to treatment should the infant qualify for the study.

Subjects are eligible for screening if any form of non-invasive support is instituted within 30 minutes of birth and the investigator feels it is safe to switch the subject to study nCPAP (or if the subject is already on nCPAP). After informed consent is obtained, subjects not already on study nCPAP should be switched to study nCPAP/interface for screening. If, within the first 6 hours after birth, the subject is stable for ≥ 15 minutes on study nCPAP of 5 to 7 cm H₂O with an FiO₂ ≥ 0.25 to 0.35 to maintain an SpO₂ of 90% to 95% and meets all other inclusion/exclusion criteria, that subject may be enrolled.

8.7.5 Documentation of Respiratory Support Parameters

8.7.5.1 Documentation during the Primary and Extended Periods

From the time of randomization until completion of Study Day 7, respiratory support parameters must be documented in the study eCRF. For each intubation and change in respiratory support, the following must be documented:

- a. Date and time
- b. The type of respiratory support and mode
- c. The reason for each intubation and change of respiratory support

8.7.5.2 Documentation during Final Period

From Study Day 8 until the subject completes the study (36 weeks PMA [or 28 days of life, whichever is later], discharged, transferred, or dies, whichever occurs first), the date and time of each intubation and change of respiratory support must be documented in the study eCRF. If the subject is discharged or transferred to another hospital prior to 36 weeks PMA, the time of discharge or transfer will be documented in the study eCRF. If the subject is on respiratory support at the time of discharge or transfer, the type of respiratory support and the mode must be documented in the study eCRF.

8.7.5.3 Documentation during Longer-Term Follow-up Phase

During the longer-term follow-up phase, the total amount of time on each ventilatory support mode, occurrence of respiratory syncytial virus (RSV) infection (as determined by specific Polymerase Chain Reaction [PCR]) and administration of Synagis for the first time must be documented in the study eCRF at 6 (via telephone or report), and 12 months corrected age.

8.8 Technical Performance of the Device

The following parameters will be captured in the eCRF to document the performance of the device:

- a. Information from touchscreen display:
 1. Total treatment duration
 2. Total amount dispensed
 3. Number of pauses
 4. Total time paused
- b. Issues associated with device tubing (eg, CPAP tubing detachments, aerosol tube detachments, proximal pressure port obstruction, aerosol tube condensate obstruction).
 5. The number of the detachments that are intentional and unintentional will also be recorded
- c. Aerosol or study drug (liquid) leakage before the subject interface (eg, disconnect of the inspiratory circuitry).
- d. Occurrence of alarm signals before, during, or after treatment.
- e. Any automatic system shutdowns with an associated error code.
- f. Inability to maintain nCPAP, with a description.
- g. ADS temperature alerts (high or low).

8.9 Initial Discharge

The date of the subject's initial discharge from the hospital will be recorded, regardless of when it occurs.

8.10 6 and 12-Month Follow-up

8.10.1 Health Assessment

The subject's overall health and the occurrence of any respiratory diseases since the previous assessment will be recorded at 6- and 12-months corrected age.

8.10.2 Abbreviated Physical and Neurological Exam

An abbreviated physical and neurological exam will occur at 12 months corrected age.

In addition, growth parameters (length, weight, head circumference) will be recorded at 12 months corrected age.

8.10.3 Hospitalizations and Emergency/Urgent Care Visits

The number of hospitalizations and emergency/urgent care visits after the initial discharge, when they occurred, the duration of visits, and the reason will be reported from 36 weeks PMA to the 6- and 12-month corrected age follow-up period visits.

8.11 End of Study Definition

A subject is considered to have completed the study if he or she has completed all phases of the study through initial discharge, including the last scheduled procedure at 36 weeks PMA (or 28 days of life, whichever is later), as shown in the Schedule of Activities (SoA), Section 1.2. It does not include the 6- and 12-month follow-up visits.

The end of the study is defined as completion of the last visit or procedure for the last subject in the trial (last subject/last visit).

9 ADVERSE EVENT REPORTING

Information regarding the occurrence of AEs will be assessed from the time of randomization until completion of 36 weeks PMA/Final Visit. Incidence of ADEs will be assessed from the time of randomization until completion of Study Day 7.

For purposes of this study, the following will be considered AEs of special interest:

1. AEs during the dosing period (ie, peri-dosing events), defined as the following AEs with an onset time \leq 2 hours from the time of initiating study treatment:
 - Apnea (lack of inspiratory air movement sustained for \geq 20 seconds and coincident with at least one of the following: $\text{SpO}_2 < 80\%$, $\text{HR} < 100 \text{ bpm}$, requirement for PPV administered manually or mechanically through any patient interface)
 - Bradycardia (heart rate $< 100 \text{ bpm}$ sustained for ≥ 20 seconds)
 - Desaturation ($\text{SpO}_2 < 80\%$ sustained for ≥ 20 seconds)
 - Gagging/regurgitation
 - Pallor
2. Complications related to placement of the patient interface as identified by the following:
 - Bleeding
 - Apparent obstruction of the nares
 - Occlusion of the interface requiring removal and replacement
 - Nasal irritation (erythema of nares or septum, inflammation of nares or septum)
3. Air leak is considered an AE of special interest if it occurs at any time during the study. Examples of air leak include the following:
 - Pneumothorax
 - PIE
 - Pneumomediastinum
 - Pneumopericardium
 - Subcutaneous emphysema

Complications of prematurity, including IVH, PVL, pulmonary hemorrhage, apnea, NEC, PDA, acquired sepsis, and ROP, will be summarized but are not considered AEs of special interest.

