This study is a multinational, multicenter, double-blind (masked), parallel group, randomized, controlled study to evaluate the safety and efficacy of lucinactant for inhalation in conjunction with nCPAP compared with nCPAP alone, in preterm neonates 26 to 32 completed weeks PMA who are being cared for in a neonatal intensive care unit (NICU), who had successful implementation of non-invasive respiratory support or ventilation within 30 minutes of birth, and who are candidates for SRT. It is strongly recommended that the initial mode of support is study nCPAP (bubble nCPAP); however, other non-invasive modes are acceptable if the investigator feels it is safe to switch the subject to study nCPAP following consent and screening. There will be 2 phases in the study, a primary phase through 36 weeks PMA or 28 days of life (whichever is longer), and a longer-term follow-up phase through 12 months corrected age. Data will be analyzed and reported at the completion of each respective study phase.

Before study enrollment, legally authorized representatives will provide a signed informed consent form (ICF) for each potential subject; it is recommended that informed consent be obtained antenatally. Qualification for study enrollment will be established after confirmation that the subject has met all of the inclusion criteria and none of the exclusion criteria. The clinical criteria for enrollment may be met prior to

informed consent being obtained; however, no study-specific procedures that are not part of the required care of the subject at the institution may be performed until the informed consent has been provided by a legally authorized representative of the subject. Time to treatment is potentially an important factor in the success of non-invasive delivery of surfactant. Because of this and other operational factors, antenatal consent should be obtained where permitted.

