6 STUDY TREATMENT DOSING AND ADMINISTRATION

Preterm neonates who meet all inclusion criteria and no exclusion criteria will be considered to be potential subjects. As soon as study qualification has been confirmed and parental consent obtained, subjects will be randomized to 1 of 2 treatment groups. Time to treatment is potentially an important factor in the success of non-invasive delivery of surfactant. Because of this and other operational factors, antenatal consent should be obtained where permitted. Subjects for which parental consent has been obtained but are not randomized are considered screen failures.

All subjects will receive standard neonatal care in the NICU. Subjects randomized to the active group and the first 2 subjects at each site will receive reconstituted lucinactant delivered via the ADS in conjunction with nCPAP. Subjects randomized to the control group will receive nCPAP only. In order to maintain masking, control subjects will receive “sham” study drug treatment: the ADS will be brought to the bedside but will not be used and no active study drug will be administered. All subjects, including controls, may receive up to 3 repeat treatments if repeat treatment criteria are met. Subjects randomized to the active treatment group may be administered up to an additional 3 treatments of lucinactant for inhalation within 36 hours of randomization. Subjects randomized to control may receive up to an additional 3 sham treatments while receiving nCPAP within 36 hours of randomization.

To maintain masking, study treatment will occur behind a visual barrier. Each site will develop a site-specific blinding plan based upon general procedures provided by Windtree. All staff designated as “blinded” will not be allowed to observe preparation of study materials, setup of the device, or to observe the subject during study treatment through discontinuation and removal of equipment unless an emergent condition develops. The sponsor (as applicable) and the subject’s legally authorized representative will also remain masked. (See also Section 6.6.) For the first 2 open-label active study treatments, blinding procedures should still be followed to ensure the feasibility of the site’s blinding plan.

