9.1.3 Adverse Event Procedures

All AEs (and ADEs) are to be assessed in all subjects throughout the study period (from enrollment to study withdrawal or completion) and documented in the study eCRF. Each AE should be reported spontaneously or in response to general, non-directed discussion with the attending nurse or physician (eg, has there been any change in subject status since the last assessment period?). For each AE, the investigator should obtain all information required to complete the AE page of the eCRF, in accordance with eCRF completion guidelines (provided separately by Windtree).

All AEs, regardless of seriousness, severity, or relationship to study participation, must be recorded (using medical terminology) in the source document and on the AE page of the eCRF. Whenever possible, diagnoses should be given when signs and symptoms are due to a common etiology.

All AEs must be followed until resolution or until a stable clinical end-point is reached, or for at least 30 days after the subject's last day in the study if an AE is ongoing at the time the subject completes the study. All measures required for AE management and the ultimate outcome of the AE must be recorded in the source document and reported on the AE page of the eCRF.

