6.3 Adverse Events

All treatment-emergent AEs (TEAEs; AEs occurring at or after randomization) will be coded by preferred term and system organ class (SOC) from the Medical Dictionary for Regulatory

Activities (MedDRA), version 16.1 or above, and will be reviewed by the medical monitor or designee. All TEAEs will be summarized as categorical variables (frequency and percent) by treatment group unless otherwise indicated. TEAEs that are related to the device (ADEs) will be summarized with all AEs and separately. TEAEs will not be compared between treatment groups.

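### Harm between the post-consent switch to study nCPAP and randomization is not collected as an adverse event, and for screen failures no adverse event collection is described at all

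*Protocol*

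**What the plan says.** **The AE window.** Protocol Section 9 states: "Information regarding the occurrence of AEs will be assessed from the time of randomization until completion of 36 weeks PMA/Final Visit". For device effects it adds: "Incidence of ADEs will be assessed from the time of randomization until completion of Study Day 7". The schedule of activities (Section 1.2) marks AEs and ADEs in the Primary, Extended and Final Periods and leaves Screening blank. SAP 6.3 uses the same starting point: "All treatment-emergent AEs (TEAEs; AEs occurring at or after randomization". Section 9.1.3 words the window differently: "All AEs (and ADEs) are to be assessed in all subjects throughout the study period (from enrollment to study withdrawal or completion".

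**The switch.** Section 8.7.4 reads: "After informed consent is obtained, subjects not already on study nCPAP should be switched to study nCPAP/interface for screening". The infant must then be stable on that device for 15 minutes or more, within set pressure and oxygen limits, before enrollment is allowed. Section 8.7.1 defines study nCPAP as the particular bubble device and interface that the sponsor supplies.

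**The risk.** Section 8.7.3 says that "each change in modality results in transient removal of positive airway pressure from the subject, which may cause alveolar derecruitment and subsequent respiratory deterioration", and it calls this a safety risk.

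**Infants who do not proceed.** Section 6: "Subjects for which parental consent has been obtained but are not randomized are considered screen failures".

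**The concern.** Under Section 8.7.4 the switch is directed by the protocol and takes place after consent, with a device the sponsor supplies. The protocol itself names a mechanism by which such a change could harm the infant. Yet the AE window opens only later, at randomization.

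The infants harmed most are the least likely to reach that point. Intubation before enrollment and an air leak at baseline are both exclusions (Section 5.3, items 9 and 11). A lasting rise in oxygen need above the inclusion limit also blocks qualification while it persists (Section 5.2, item 6). The safety record would then hold mainly infants who tolerated the switch. The DMC works from AEs, ADEs, SAE case reviews and tables of the safety endpoints (Section 7.1), so it could miss a problem with this step.

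**Working it through.** The plan states no figure on this point, so the check sets the texts side by side.

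1. **Does the switch precede randomization?** Under Section 8.7.4 it does. The order is consent, switch, at least 15 stable minutes on study nCPAP, then enrollment. Three other places point elsewhere or are unclear:
   - The Protocol synopsis allows other initial modes "if the investigator feels it is safe to switch the subject to study nCPAP following consent and screening", which puts the switch after screening.
   - SAP 2.2 says the same as the synopsis.
   - Section 6.4.1 describes connection to the study nCPAP and airway connector after its sentence on randomization. This may be the same switch or a later circuit change.

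2. **Does the Section 9.1.3 wording close the gap?** Not clearly. It opens the window at enrollment. Section 6.5 treats randomization and enrollment as one act in the central allocation system, and Section 8.7.4 places enrollment after the switch. On that reading both windows open after the switch. On any other reading, Sections 9 and 9.1.3 contradict each other.

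3. **Where would an event between switch and randomization be recorded?**

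| Infant | AE or ADE record | Other record described |
|---|---|---|
| Later randomized | None, because onset precedes the window | Medical history from birth to randomization (Section 8.5), summarized by group (SAP 3.2.2) |
| Not randomized (screen failure) | None described | SAE capture unspecified: Section 9.1.4 gives no start point |

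   Medical history is a weaker record. Section 9.1 requires severity, outcome, action taken and relationship to drug or device for each AE. Section 8.5 asks for none of these.

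4. **Could the safety analysis recover it?** No. The SAP 6.1 safety population is limited to infants given active or sham treatment, so a screen failure appears in no safety table.

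5. **Is this consistent with the rest of Section 9?** Not fully. That section makes complications of interface placement, and air leak at any time in the study, AEs of special interest. For a switched infant the study interface is first placed before AE collection begins.

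6. **Can the size be computed?** No. That would need the number consented, the number switched and an event rate around the switch. The documents give none of these. SAP 2.1 gives only screening totals, and they disagree: it states 8 screened per enrolled, but 720 screened for about 130 enrolled is 720 / 130 = 5.5, and 720 / 8 = 90 enrolled.

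**The case against.** **Other routes may catch these events.** Section 9.1.4 requires notice of SAEs whether or not they relate to the study and does not tie this to randomization. Section 9.1.5 likewise gives no start date for unanticipated device effects. Section 8.7.2 asks that any event pointing to a need for ventilation or more support be considered as a possible AE. Respiratory support is recorded from Screening, and concomitant therapies from birth. This stands in part. A reader might infer that such harm is never counted or leaves no record, and the documents do not support that: randomized infants have a medical history entry, and SAE reporting in screen failures is left open, not ruled out. But none of these provisions opens an AE window before randomization or says that screen failures are covered.

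**The timing is not settled.** If the switch follows randomization, harm from it falls inside the window. This stands, and it is why the timing conflict belongs to the finding. Where a site follows Section 8.7.4 the gap is real.

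**The risk sentence is taken from another argument.** Section 8.7.3 uses it to discourage moves away from study nCPAP. That is so, but its wording and its mechanism cover every change of modality.

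**Few infants may be affected.** The switch applies only to infants not already on study nCPAP, starting on bubble nCPAP is strongly recommended, the investigator must judge the switch safe, and the device is commercially available. All of this stands and limits the likely scale.

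**No randomized comparison depends on it.** Correct. The point concerns the completeness of the safety record.

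**Conclusion.** The concern holds in a limited form. If Section 8.7.4 is followed, harm with onset between the switch and randomization is not collected as an AE or ADE. It can appear only as medical history in infants later randomized. In screen failures no AE collection is described and SAE capture is unspecified. The documents also conflict on the timing of the switch and on the opening of the AE window.

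The conclusion rests on two readings: that the order in Section 8.7.4 is the one used, and that enrollment means randomization, as Section 6.5 suggests.

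No magnitude can be given. A reader might be tempted to size the gap from the 8:1 screening ratio in SAP 2.1, but that ratio does not match the counts beside it and says nothing about how many infants were consented or switched. Nor do the documents show that any infant was harmed in this interval. The finding merits a change because the change is cheap and adds safety data on a study-directed step, not because a treatment comparison is at risk.

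**What to change.** - In Sections 9 and 9.1.3 and in the schedule of activities, start AE and SAE recording at the first study-specific procedure after consent. State that this includes consented infants who are switched to study nCPAP but not randomized.
- State the same start point in Section 9.1.4.
- Keep SAP 6.3's definition of treatment-emergent events, from randomization on, for the comparison between arms. List earlier events separately, including those in screen failures, and put them in the reports to the DMC.
- Reconcile the Protocol synopsis, Sections 6.4.1 and 8.7.4 and SAP 2.2 on when the switch occurs, and Sections 9 and 9.1.3 on when the AE window opens.

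SAP 2.1 reports that enrollment ended after 12 subjects. For this trial the practical step is to check whether any consented infant had an event between switch and randomization, report it if so, and otherwise state the limitation. The wording changes serve later protocols.

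The cost is a short AE record for infants switched but not randomized, plus the wording changes. The arm comparison is unchanged.
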